Primary objective	To determine treatment effect on caregiver burden measured as Resource Utilization Dementia (RUD), and the Relative Stress Scale (RSS). Based on the correlation coefficient, we will use all three subcategories of RUD separately. Total score will be used when assessing RSS. Further, we will evaluate the economic consequences of the treatment by calculating Incremental Cost-Effectiveness Ratio (ICER) and quality adjusted life years (QALY).
Secondary objectives	To determine treatment effect on quality of life (QoL) using the European Quality of Life – 5 dimension – 5 levels (EQ-5D-5L), EQ-5D-VAS scale, Quality of Life in Alzheimer's disease scale (QoL-AD); neuropsychiatric symptoms in dementia using the Neuropsychiatric Inventory 12 item (NPI-12), agitation in dementia using Cohen-Mansfield Agitation Inventory (CMAI), depression in old age (Geriatric Depression Scale - GDS), functional level for instrumental and personal activities (ADL and IADL), and the caregiver rating of clinical meaningful change using Clinical Global Impression of Change (CGIC).
Exploratory objectives	
In line with total score of RSS, we will also explore the treatment effect on both single and clustered items.
 
In line with total score of QoL based instruments (EQ-5D-5L, QoL-AD, QoL – CG, GDS), we will also explore the treatment effect on both single and clustered items
 
To assess the effect on pain in dementia using the Mobilization – Observation – Behavior – Intensity Dementia Pain Scale (MOBID-2)
 
To determine the characteristics of the dyads who had the highest improvement in RUD and RSS, i.e., those who benefitted the most from the intervention.

Endpoints	
Primary endpoint: Change in caregiver burden and informal care time among the caregivers in the intervention group during active intervention period, and the follow-up. Change in Cost-efficiency of treatment.
 
Secondary endpoint: Improvement in QoL for both PwD and caregivers. Reduction in neuropsychiatric symptoms in dementia and functional level during active intervention period and follow-up.
 
Exploratory endpoint: Reduction in pain during active intervention period.

Treatments	Allocation to municipal coordinator delivering the multicomponent LIVE intervention (L:learning, I: innovation, V: volunteering and E:empowerment) or care as usual.
Number of patients	315 dyads will be screened to achieve at least 105 dyads per municipality.

Safety analysis	Not applicable

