Planned enrolment	3 municipalities and 9 municipality districts

Sample size estimation

The required sample size calculated before recruitment of participants aimed to detect a difference of 7 h/week for the primary outcome RUD. Based on the literature[4], we assumed that the number of hours of informal care is 46 h/week with a standard deviation (SD) of 20 h/week. With 80% power and a significance level of 5%, the required sample size was estimated to be 260 dyads. To allow for 20% loss to follow-up, a total of 315 dyads, equaling 105 per municipality, must be included.

The post-hoc sample size calculations based on the outcome PADL showed that by treating the study as an individually randomized stepped wedge design[3], with 3 intervention sequences, 5 periods, effect size of 7h/week, outcome variance of 400, significance level of 5% and within-individual correlation of 0.1075 over the 24 month trial would require a total of 240 dyads to be included. To allow for 20% loss to follow-up, the sample size must reach 288 dyads.

Randomization, blinding and unblinding procedures

Block randomization was performed using a computerized random number generator to allocate individual dyads to the three intervention sequences. We will apply stratification to secure that about one third of the dyads in each treatment sequence will be recruited from each municipality. Research assistants, researchers conducting the analyses and other study personal conducting data collection will be blinded to the randomization order, the dyads will be blinded to group allocation until contacted by their coordinator at start of the intervention period. Given the practice change of the intervention, the municipality home care services and coordinators will be informed about allocation sequence when their clusters entered the intervention period.

Analysis Sets

Full Analysis Set (FAS)

The intention-to-treat population includes all randomized dyads who were assigned a coordinator by the municipality. The dyads will be analyzed separately (i.e., PwD and caregiver), dependent on outcome of interest.

This will be the primary analysis set for baseline summary statistics of demographics, primary, secondary and exploratory efficacy analysis as elaborated in section 10.

Municipal coordinator set (MCS)

All coordinators in all municipality districts

Usage overview of analysis sets table

Analyses	FAS	MCS	
Disposition			
Demographics and background	x		
Medical history			

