Efficacy: primary	x		
Efficacy: secondary	x		x
Efficacy: other	x	x	x

General Statistical Methods and Definitions

General statistical methods

The statistical analysis will be presented by treatment group for the different analysis sets as outlined in section 4.

Stepped wedge design (SWD) do not strictly feature a treatment and control group, and thus, the summary statistics will include all participants at baseline, and the characteristics according to intervention sequences.

Continuous variables will be summarized using descriptive statistics (means and interquartile ranges), and categorical variables will be presented by frequencies and percentages. A table will present the number of caregivers and PwD with the following data: missing values, mean, median, standard deviation and confidence intervals.

Means and median as well as percentages will be presented with 1 additional decimal place and standard deviation by 2 additional decimals.

If the number of PwD or caregivers in a category is 0, then percentage will not be displayed.

P-values will be reported to 3 decimal places.

Unless otherwise specified, all statistical tests will be two-sided.

Causal model

Due to the longitudinal structure of the collected trial data, we considered the following linear mixed model to estimate and identify the treatment effect due to the intervention. Our SWD, consisting of $j = 3$ municipalities and 3 steps, is a closed cohort design, and thus, time related confounders are important to adjust for [5] when assessing treatment effect.

Mixed-effects regression is one of the most common approaches when estimating the intervention effect in SWD [6, 7]. In our design, we will consider the following model as our primary analysis model, assuming a constant treatment effect.

$$(1) Y_{ijt} = \beta_0 + O_{ijt}\beta_1 + X_{ijt}\beta_2 + b_i + \epsilon_{ijt}$$

where notation Y_{ijt} refers to the primary outcome caregiver burden (RUD and RSS), elaborated in section 3 Study Design, for individual i nested in municipality j at time point t . O_{ijt} is the treatment indicator (effect of receiving assistance from a municipality coordinator) and β_1 is the average treatment effect parameter of interest. Since the study collects repeated observations from the same participants, we consider a longitudinal regression model that adjusts for participant-level random effect, $b_i \sim N(0, \sigma_b^2)$, which corresponds to a compound symmetric correlation structure.

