$\epsilon_{ijt} \sim N(0, \sigma_\epsilon^2)$ represents random error that changes across t and i .

X_{ijt} constitutes control variables which are demographic, socio-economic and clinical confounders (age, sex, caregiver marital status, work status, ADL function), and stratification variables used in the design stage.

Due to the non-normal distribution of hours and costs we will use both linear mixed-effects, as well as general lineal mixed regression model for assessing both primary variables. For RSS, and other continuous variables, we use Linear Mixed regression model. Log-transformation of the outcome will also be considered to address potential non-normality in the response.

Intervention effect

In secondary analysis, we will further examine the extent to which the treatment effect will depend on the calendar time when COVID lockdown happened, and the potential for delayed effect. We collectively refer these effects as heterogeneous treatment effect, and provide a schematic illustration following Section 3.2 of Li et al. (2020) [6]. The rationale is that there the lockdown during the pandemic may contribute to change in the intervention effect. In addition, the intervention may be most effective when it is first introduced, and the sustained effect may be smaller. Therefore, when modelling the intervention effect, we will allow for heterogeneous effect and assess the robustness of our primary analysis. The table below shows how the intervention effect can differ between periods (t) across different groups (g). The deltas (δ) constitute the intervention effect, and their subscript defines heterogeneous effects where δ_0 is the pre-lockdown intervention effect, δ_0^* is the intervention effect post-lockdown, and δ_1^* is the follow-up post-lockdown treatment effect.

When modelling the intervention effect, we will test the null-hypothesis (H_0)

$$\delta_0 = \delta_0^* = \delta_1^*$$

	$t = 1$	$t = 2$	$t = 3$	$t = 4$
$g = 3$			δ_0^*	δ_1^*
$g = 2$		δ_0^*	δ_1^*	δ_1^*
$g = 1$	δ_0	δ_1^*	δ_1^*	δ_1^*

Economic evaluation

If we identify an average treatment effect on one of the primary and secondary outcomes, we will use cost-efficiency (CEA) and cost-utility analysis (CUA) to evaluate the economic effects of the LIVE treatment.

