- Formal caregiver (whether dyads are receiving care by home nursing)
- Categories of caregiver burden intensity
- Categories of dementia diagnoses

Results from subgroups will be presented for the primary analyses.

Observation and analysis times

Study periods

Timeline															
Groups/participants	Inclusion period	Control group			Kristiansand 3, N=35			Bærum 3, N=35			Bergen 3, N=35				
					Kristiansand 2, N=35										
					Bærum 2, N=35										
					Bergen 2, N=35										
		Kristiansand 1, N=35						Follow up							
Number of months		0	1 2	3 4	5 6	7 8	9 10	11 12	13 14	15 16	17 18	19 20	21 22	23 24	
Date		01.09 2019		01.03 2020		01.09 2020		01.03 2021							

		STUDY PERIOD							
		Enrollment		Allocation	Post-allocation				Close-out
TIMEPOINT	-t	0		t1	t2	t3	t4	t5	
ENROLLMENT:									
Eligibilityscreen	x								
Informed consent	x								
Allocation		x							
INTERVENTIONS:									
1st group			x	x					
2nd group				x	x				
3rd group					x	x			
ASSESSMENTS:									
Baseline variables			x						
Outcome variables				x	x	x	x	x	

The stepped wedge randomized control design. A) The randomization in time takes place at month 0. First group (red) is in the intervention period from month 1 to 6, second group (yellow) from month 7 to 12, third group (green) from month 13 to 18. Implementation seminars will be held at month 0, 6 and 12, midway evaluation at month 3, 9 and 15. Data will be collected at baseline (month 0), after first intervention period (month 6-7), after second intervention period (month 12-13), after third intervention period (month 18-19) and at end of study at 24 months. B) Schedule of enrollment, interventions and assessments over the study period.

Demographics and Background Characteristics

Demographics and baseline characteristics

The following demographic characteristics will be presented descriptively and listed for both PwD and caregiver:

- Sex (male, female)
- Age in years
- Marital status (spouse, child)
- Work status (employed, unemployed, retired)
- Number of co-caregivers
- MMSE total score
- RUD (number of care hours the last 30 days)
- RSS total score
- NPI total score
- QoL total score

Date of informed consent and protocol version will be listed

Medical history

We will provide information on the number of years since formal diagnosis of dementia together with descriptive statistics.

Exposure and Compliance

Treatment groups

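### The set labelled intention-to-treat, used for primary efficacy, admits only randomised dyads that were assigned a coordinator, and the coordinator is the treatment

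*SAP*

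**What the plan says.** All references are to the SAP.

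- **Analysis Sets, Full Analysis Set (FAS):** "The intention-to-treat population includes all randomized dyads who were assigned a coordinator by the municipality". On its use: "This will be the primary analysis set for baseline summary statistics of demographics, primary, secondary and exploratory efficacy analysis". The only other set, the municipal coordinator set, consists of coordinators and not dyads.
- **Study Design, Treatments:** "Allocation to municipal coordinator delivering the multicomponent LIVE intervention", as against care as usual.
- **Causal model:** the treatment indicator O_ijt in model (1) is glossed as the "effect of receiving assistance from a municipality coordinator".
- **Randomization, blinding and unblinding procedures:** individual dyads are randomised to three sequences. On timing, "the dyads will be blinded to group allocation until contacted by their coordinator at start of the intervention period", and "coordinators will be informed about allocation sequence when their clusters entered the intervention period".
- **Study periods:** randomisation is at month 0 and the first group starts at month 1; then "second group (yellow) from month 7 to 12, third group (green) from month 13 to 18".
- **Exposure and Compliance, Treatment groups:** the same definition of assignment is carried over, and departures from the randomised sequence in the first lockdown are acknowledged.

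No section dates the assignment of a coordinator or says how many randomised dyads had none.

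**The concern.** An intention-to-treat set is fixed by randomisation alone. Here membership also requires the municipality to have supplied the person who delivers the treatment. A dyad that was randomised but never given a coordinator drops out of the primary analysis, and nothing in the plan would show what its removal does to the estimate.

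The stepped-wedge layout can add a second problem. If assignment takes place when a sequence starts, a sequence 3 dyad lost at month 9 is deleted with its control-period visits, while a sequence 1 dyad lost at the same month stays in. Membership would then depend on an event after randomisation whose waiting time differs by randomised sequence. The rule would also discard control visits that model (1) can use and that the Missing data section, which relies on a missing-at-random argument, would keep.

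At stake is whether the primary result has the protection of randomisation that its label claims.

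**Working it through.** **1. The definitions side by side.** The treatment is allocation to a coordinator. The indicator is assistance from a coordinator. The efficacy set is randomised dyads assigned a coordinator. The set is thus conditioned on the treatment provider being in place. This step needs no arithmetic and no assumption about dates.

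**2. The plan's own figure.** With a difference of 7 h/week, SD 20, 80% power and two-sided 5% (Sample size estimation), n per arm = 2 × (1.960 + 0.842)² × 400 / 49 = 128.1, or 129 rounded up. That gives 258 in total against the stated 260, so the figure reproduces. The point does not depend on it; it only confirms the effect size and variance used below.

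**3. How many dyads the rule could remove.** Assumptions:
- assignment at the sequence's own start, on the original Study periods schedule (m = 0, 6 and 12 months of waiting)
- 105 dyads per sequence (315 / 3)
- loss L accruing evenly over 24 months, with the SAP's 20% and, as a range, 30%

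Removed = 105 × (1 − (1 − L)^(m/24)).

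| L | Sequence 1 | Sequence 2 | Sequence 3 | Total of 315 |
|---|---|---|---|---|
| 20% | 0 | 5.7 (5.4%) | 11.1 (10.6%) | 16.8 (5.3%) |
| 30% | 0 | 9.0 (8.5%) | 17.2 (16.3%) | 26.1 (8.3%) |

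If every dyad was assigned at month 0, all of these become 0. The April 2020 postponements would change the waiting times, and the SAP does not give the amended dates. The grid under Intervention effect carries no dates, so it cannot confirm these starts.

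**4. Bias in β₁ on that reading.** Expected generalised least-squares estimates were computed for 3 sequences and 5 visits (months 0, 6, 12, 18, 24), with fixed effects for period, variance 400, compound symmetry with correlation 0.1075 (the SAP's value) or 0.5 (assumed), and a true effect of −7. A leaver's last visit is shifted by an assumed D. With period terms, the all-randomised set returns exactly −7, because loss is the same in every sequence and the period terms absorb the shift. The departure of the coordinator-assigned set from −7 is therefore its bias:

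| L | Correlation | D = +10 h/week | D = +20 h/week |
|---|---|---|---|
| 20% | 0.1075 | +0.137 | +0.275 |
| 20% | 0.5 | +0.122 | +0.243 |
| 30% | 0.1075 | +0.216 | +0.431 |
| 30% | 0.5 | +0.192 | +0.385 |

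As a share of the effect, this runs from 0.122 / 7 = 2% to 0.431 / 7 = 6%; it is 8 to 26% of a standard error. With negative D every sign reverses. Leavers with higher care time push the estimate towards less benefit, and leavers with lower care time towards more.

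No bias is quoted for model (1) as printed, without period terms. There the all-randomised estimate is itself off by −0.06 or +0.24 h/week (20% loss, D = +10, correlation 0.1075 or 0.5), so a difference between the two sets is not a bias.

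**5. What the all-randomised set costs.** The standard error is 1.77 h/week for both sets (20% loss, correlation 0.1075, period terms). Dyads that stay in without a coordinator dilute the effect: −7 × 0.95 = −6.65 if 5% are unserved, and −7 × 0.90 = −6.30 if 10% are. Both shares are assumed.

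**The case against.** The strongest reply is that the timing is inferred. The text says when coordinators learn the sequence and when dyads are contacted; neither is the date of assignment. Being contacted by one's own coordinator is compatible with that coordinator having been named at month 0. The criterion is assignment, not receipt of service; one coordinator is planned per dyad; and every sequence eventually receives the intervention. The condition may therefore exclude few dyads or none. This stands, so the exclusions by sequence remain conditional.

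A second reply is that the bias is small. The larger values need leavers to differ by 20 h/week, a full SD, which nothing in the SAP supports. When dropout was instead simulated to depend on latent burden (log-odds 0.5 or 1.0 per SD, no treatment effect), the two sets' estimates differed by no more than about 0.1 h/week. The covariate adjustment planned under Missing data might reduce it further. This also stands. Non-assignment tied to the lockdown or to the course of burden was not modelled and could behave differently.

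A reader might infer that the primary result is materially biased, or that later sequences did lose more dyads from the set. The SAP supports neither: it gives no assignment date, no count of dyads without a coordinator, and nothing on whether leavers carry more or less care time.

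None of this rescues the label. Either the condition excludes someone, and the set is not intention-to-treat, or it excludes no one and has no purpose.

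**Conclusion.** The point holds in a limited form, and the definition should be corrected. The label is wrong for any randomised dyad without a coordinator, on the text alone. Exclusion that differs by sequence follows only if assignment happens at each sequence's start. Under that reading, the original schedule and even loss, the bias with period terms is 0.12 to 0.22 h/week for an assumed 10 h/week difference in leavers and 0.24 to 0.43 for 20. Its direction is unknown and it is small against 7 h/week. Confidence is moderate, because the assignment date and the number of unserved dyads are not in the document.

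**What to change.** - Define the FAS as all randomised dyads with at least one outcome assessment (month 0 counts), analysed by randomised sequence whether or not a coordinator was assigned.
- Code O_ijt from the planned start for that sequence within that municipality under the approved April 2020 change, and list those dates. One start per sequence will not do, because Changes to the study protocol describes postponement by municipality.
- Keep the coordinator-assigned set as a sensitivity set under another name, and state when assignment took place.
- Report, by sequence, how many randomised dyads had no coordinator. If all were assigned at month 0, simply delete the condition.

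**Cost.** Precision is essentially unchanged, but this is a change of estimand as well as wording. The dilution shown above, 0.35 or 0.70 h/week for 5% or 10% unserved, can exceed the bias removed, so the two sets should be reported side by side.

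**A separate model point, which adds no weight to this one.** Model (1) shows no period term although the Causal model section calls for adjustment for time-related confounding, and ADL function is an undated covariate that is also a secondary outcome. Add fixed effects for the five assessment periods and use month-0 covariate values. Period terms raise the standard error from 1.04 to 1.77 h/week (20% loss, correlation 0.1075); 7 / 1.77 is still about 4 standard errors.

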In cost-effectiveness analysis the effect is measured in health units (or other outcome measures depending on the context). The outcomes are common health measures in natural units, and the results are presented as cost per effect unit/outcome measure. In cost-utility analysis, also called cost per QALY analysis, the effect is measured as quality-adjusted life years (QALYs) on a scale of 0 (death) and 1 (full health). A quality-adjusted life year (QALY) captures both life years gained and improved health as a result of treatment [8, 9].

The economic evaluation will be measured at society level.

Costs and QALYs will be measured for each phase of 6 months

The cost-effective analysis will relate the difference in total mean costs at societal level per 6 months between all intervention -and usual care phases to the difference in RUD, RSS, QoLs, QALYs, NPI, function level such as ADL and IADL

The analysis will use a discounting rate at 3.5%.

Following other costs studies calculating RUD in an advanced economy setting, our analysis will use 35% of the Norwegian average income to value lost leisure time for retired caregiver.

The primary economic evaluation will use the opportunity cost method to assess the costs of informal caregiving. For a sensitivity analysis, the replacement cost will be used.

Unit costs will be based on information from Statistics Norway and information from the primary health care institutions in each municipalities.

Covariates and strata

In the main statistical analyses, the following covariates are used for both caregivers and PwD.

For PwD: Age, sex, marital status, cohabitation status, number of co-caregivers, clinical characteristics of dementia (dementia etiology, neuropsychiatric symptoms, functional level)

For Caregivers: Age, sex, marital status, cohabitation status, numbers of co-caregivers involved in caregiving for the PwD, work status, use of health care services,

Groups, municipalities

Municipalities will be grouped in the main analysis and used as an adjustment variable (fixed effects). This is not the case for district municipalities as we consider that the dyads are similar within municipalities

Subgroups

In subgroup analyses, the following covariates will be used to define relevant subgroups:

- Gender (male, female)
- Work (retired and working caregivers)
- Caregiver relation (spouse, children)
- Residency (living alone, or with caregiver)

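### The primary mixed model has no period term, although the SAP says time must be accounted for, so the treatment coefficient can absorb secular and Covid-19 change

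*SAP*

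**What the plan says.** - **Need for time adjustment.** The Causal model section says that, because the design is a closed cohort, "time related confounders are important to adjust for".
- **Primary model.** The same section then says: "In our design, we will consider the following model as our primary analysis model, assuming a constant treatment effect". Equation (1) has five parts: intercept, O times β1, X times β2, a participant random intercept and a residual.
- **Content of X.** X "constitutes control variables which are demographic, socio-economic and clinical confounders (age, sex, caregiver marital status, work status, ADL function), and stratification variables". The lists under Covariates and strata add items such as cohabitation, co-caregivers, neuropsychiatric symptoms and use of health care services. Municipality is the only fixed-effect grouping named. None of these is a period, wave, calendar-time or lockdown term.
- **Where calendar time appears.** Under Intervention effect, a secondary analysis asks how far the "treatment effect will depend on the calendar time when COVID lockdown happened". That lets the effect vary through three deltas. No main effect of time on the outcome is stated.
- **Treatment in follow-up.** The delta table keeps a treatment effect in every cell after crossover. The primary endpoint is "Change in caregiver burden and informal care time among the caregivers in the intervention group during active intervention period, and the follow-up". Both imply that treatment stays on, but the definition of O does not say how follow-up is coded.
- **Economic evaluation.** It uses the "difference in total mean costs at societal level per 6 months between all intervention -and usual care phases" and mentions no period adjustment.

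**The concern.** In a stepped-wedge trial the treated proportion rises with calendar time by design. Randomising the crossover time protects the treatment comparison only if dyads are compared within the same period. Without a period term, part of β1 is a before-after contrast. The random intercept removes stable differences between participants, but not change shared by all of them.

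Such change is likely here: the cohort has a progressive disease and is followed for 24 months, and the SAP's Modification History describes a pandemic during the trial. A rising burden would hide a real benefit or show false harm. A falling burden, or a lasting drop in the Covid-19 period, would create false benefit. If the heterogeneous-effect model also lacks period terms, a plain time trend makes the deltas differ and looks like a changed treatment effect.

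**Working it through.** **Inputs.** Sample size estimation: 3 sequences, 5 periods, variance 400, within-individual correlation ρ = 0.1075, target 7 h/week, 315 dyads with 20% loss, so 315 × 0.8 = 252. Study periods: assessments at months 0, 6-7, 12-13, 18-19 and 24, numbered t = 0 to 4, with crossovers starting in months 1, 7 and 13. Compound symmetry is the SAP's own structure. The SAP gives no trend, so all trend sizes are assumptions.

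**Method.** Under compound symmetry, generalised least squares (GLS) uses the product ⟨a,b⟩ = Σab − c·Σ(row sum of a)(row sum of b), with c = ρ/(1+4ρ) = 0.1075/1.43 = 0.0752. For a common time pattern m and no true effect, the expected β1 is (⟨O,m⟩ − k⟨1,m⟩)/(⟨O,O⟩ − k⟨1,O⟩), where k is the overall treated share. X is left out at first.

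**The plan's own figures.**
- 260 dyads: 2 × 400 × 7.849/49 = 128.1, so 129 per arm and 258 in total. This is close to the SAP's figure.
- 240 dyads: with period effects, N = (z_α/2 + z_power)² × 3 × 400(1−ρ)/(49 × 1.183). This gives 145 at 80% power and 240 at 95%. Model (1) as written (1.183 replaced by 3.450) gives 50 and 82. The SAP states no power for this calculation, but 240 fits a period-adjusted model at 95% and not model (1) at 80%, 90% or 95%.

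**Stay-on coding** (rows 01111, 00111, 00011; k = 9/15 = 0.6). Denominator: 3.6 − 2c = 3.450.
- Linear change of 1 per 6 months: 8/3.450 = 2.32. At ρ = 0.5, c = 0.1667 and 8/3.267 = 2.45.
- Lasting unit shift from t = 2, where the delta table places lockdown: 2.6/3.450 = 0.75.
- Unit shift at t = 2 only: 0.2/3.450 = 0.06. At t = 1 only: −0.8/3.450 = −0.23.
- SE at 252 dyads (84 per sequence): √(400 × 0.8925/(84 × 3.450)) = 1.11 h/week.

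| Assumed pattern, 252 dyads | Result |
|---|---|
| No effect, rise of 0.5 / 1 / 2 h/week per 6 months | 18% / 55% / 99% two-sided rejection, toward harm |
| No effect, fall of the same size | 18% / 55% / 99% false benefit, one-sided 2.5% |
| No effect, lasting drop of 1 / 2 / 3 h/week from t = 2 | 10% / 27% / 53% false benefit, one-sided 2.5% |
| True effect −7, rise of 2 / 3 h/week per 6 months | expected estimate −2.4 / −0.04; power for benefit 57% / 3% |

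Example: a drift of 1 gives z = 2.32/1.11 = 2.09 and P(Z > 1.96 − 2.09) = 55%.

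**Active-phase-only coding** (one treated cell per sequence; k = 0.2; denominator 2.4). Linear change: 0. Lasting unit shift from t = 1: 0.6/2.4 = 0.25. From t = 2: 0.2/2.4 = 0.08. Shift at one of t = 1 to 3 only: 0.4/2.4 = 0.17.

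**Absorption by X** (stay-on; covariate drifts and SDs assumed). Current age leaves the multiplier at 2.29 to 2.31. If 25% / 50% / 75% of the trend runs through current ADL, it falls to 1.67 / 1.11 / 0.55.

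**Heterogeneous model without period.** A trend of 1 per 6 months biases δ0 / δ0* / δ1* by 0.53 / 1.82 / 2.77. A lasting unit shift from t = 2 biases them by −0.14 / 0.84 / 0.85.

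**With categorical period effects** every bias above is 0. Under stay-on coding the denominator becomes 4/3 − 2c = 1.183, the SE √(357/(84 × 1.183)) = 1.90, and power for 7 h/week Φ(7/1.90 − 1.96), about 96%.

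**The case against.** - **X carries a time subscript and may absorb the trend.** Age and ADL could be current values, and the covariate lists include health-service use and neuropsychiatric symptoms, which lockdown may have changed. This stands in part: some of a trend or shift may run through them, and these last two were not modelled. They are still no substitute for a period effect. ADL and neuropsychiatric symptoms are secondary outcomes and service use may respond to the intervention, so adjusting for current values can remove part of the effect.
- **O may be 1 only during the active six months.** The equation does not exclude this, and the support for stay-on coding is indirect. Under that coding linear-trend bias is 0, but shifts still enter at 0.08 to 0.25 of their size.
- **A Covid-19 shift may have been temporary.** Under stay-on coding the bias is then 0.06 or −0.23 per unit, much less than 0.75. The false-benefit rates for lasting drops illustrate one assumed pattern.
- **The rates may not describe the test used.** They concern the test of β1 with the SD assumed for RUD hours. They do not describe the χ² test named under Primary efficacy analysis, nor RSS, for which the SAP gives no SD.
- **A period term may have been intended.** The sentence before the equation and the 240 figure point that way. If so, the written equation still has to be corrected.

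**Conclusion.** The concern holds and should be fixed before analysis. The SAP states a need for time adjustment, and its declared primary model does not meet it. The secondary analysis does not repair this, because it varies the treatment effect without adjusting the outcome level for time.

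The size depends on two things that the SAP leaves open. Under stay-on coding, which the delta table and the endpoint imply, a steady trend enters β1 at 2.32 times its change per 6 months before any absorption by X. A rise of 3 h/week per 6 months would then cancel the 7 h/week target. Under active-phase-only coding only non-linear change matters, at up to 0.25 per unit for the shifts examined. The true trend is unknown, and the figures use the planned roll-out, not the one altered by Covid-19. The contradiction itself depends on none of these assumptions.

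**What to change.** 1. Replace model (1), for every primary and secondary outcome, by Y_ijt = β0 + γ_t + O_ijt β1 + X_ijt β2 + b_i + ε_ijt, with γ_t a categorical fixed effect of measurement occasion. List it among the main-analysis covariates.
2. Keep γ_t in the heterogeneous-effect model. All three deltas stay estimable (design rank 8 of 8). Their SEs at 252 dyads go from 2.31 / 1.69 / 1.22 to 2.64 / 2.75 / 2.88 h/week.
3. State how O is coded in follow-up.
4. State that cost and QALY differences between intervention and usual-care phases use the same period adjustment.

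The cost is a few lines of SAP wording, four extra parameters in model (1) and no new data. Under stay-on coding the SE at 252 dyads rises from 1.11 to 1.90 h/week. Under the SAP's variance and correlation, about 145 dyads are enough for 80% power at 7 h/week.
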